8.4.3 Medical history

Not Applicable

8.4.4 Prior and concomitant medications

Not Applicable

8.5 Extent of exposure

8.5.1 Treatment exposure

Subjects will receive (or will have received) VIZAMYL™ intravenously prior to PET imaging, according to clinical practice.

The dose and volume administered will be summarised for prospective and retrospective images along with pooled results. Descriptive statistics will be given for the VIZAMYL™ dose (mBq) and volume administered (mL). VIZAMYL™ dose administration details will be listed.

8.5.2 Treatment compliance

Not applicable

8.6 Efficacy analyses

8.6.1 Analysis methods

All analyses will be provided in descriptive nature, counts and percentages, along with exact 95% CI, wherever applicable. All of the efficacy analyses will be based on the efficacy subject population.

8.6.2 Primary analysis

The endpoints are the diagnostic accuracy, sensitivity, specificity, PPV, and NPV. Each of the clinical image interpretations will be matched to the corresponding expert reader majority interpretation for the subject and the image interpretation will be classified as a TP, TN, FP or FN using the expert reader majority interpretation as the SOT. For example, if an image interpretation is “positive” and the expert reader majority interpretation is “positive”, the image interpretation would be classified a TP. If the expert reader majority interpretation were “negative”, however, then the image interpretation would be classified as a FP. If any reader interpretation is “probably negative” or “probably positive”, this will be considered as “negative” or “positive”, respectively in the summary tables. In addition to this primary analysis framework, a sensitivity analysis will be performed for the primary endpoints without considering “probably negative” or “probably positive” clinical image interpretations.

The numbers of TP, TN, FP, and FN images among the ≥ 200 original images will be used to calculate diagnostic accuracy:

Diagnostic accuracy =
$$\frac{\text{Number of true positives} + \text{number of true negatives}}{\text{Number of true positives} + \text{number of true negatives} + \text{Number of false positives} + \text{number of false negatives}}$$

Diagnostic accuracy will give an indication of the overall image interpretation error rate (1 minus diagnostic accuracy)

The below table provides the details and consideration of TP, TN, FP and FN.

		Expert Reader Interpretation	
		Positive	Negative
Clinical reader Interpretation	Positive	True Positive (TP)	False Positive (FP)
	Negative	False Negative (FN)	True Negative (TN)

Sensitivity, specificity, PPV, and NPV will also be calculated using the below formula:

Sensitivity =
$$\frac{\text{Number of true positives}}{\text{Number of true positives} + \text{number of false negatives}}$$

Specificity =
$$\frac{\text{Number of true negatives}}{\text{Number of true negatives} + \text{number of false positives}}$$

Positive Predictive Value =
$$\frac{\text{Number of true positives}}{\text{Number of true positives} + \text{number of false positives}}$$

Negative Predictive Value =
$$\frac{\text{Number of true negatives}}{\text{Number of true negatives} + \text{number of false negatives}}$$

The results from these calculations will be summarised with point estimates and exact 95% CIs for prospective images, retrospective images, and pooled results, separately.

In addition, the clinical reader and expert reader global classification results (positive/negative) will be summarised separately. Clinical reader and SOT classification certainty ratings (1 = low to 5 = high) will be summarised using counts and percentages for prospective images, retrospective images, and pooled results, separately. For the SOT certainty, the majority of the expert certainty ratings that formed the SOT will be used, and in the case of a tie, the lower level of certainty will be used.

Subject-level listings will be provided for the clinical reader and expert reader image evaluations. PET imaging details will also be provided in the form of listings.

8.6.3 Secondary analysis

Images for which 5 expert readers agree, 4 expert readers agree, and 3 expert readers agree will be summarised using counts and percentages.

In addition, estimates of diagnostic accuracy, sensitivity, specificity, PPV, and NPV, along with exact 95% CIs, will be provided separately for prospective images, retrospective images, and pooled results, separately, using the following variables:

- Country
- Time from training to image interpretation (<6 months, \geq 6 months)
- Specialty of the reader
 - Nuclear Medicine
 - Radiology
 - Medical Physics
 - Other
- Training method (s) used by the clinical reader (in-person, electronic, or both)
- Number of scans read by the clinical reader in practice prior to the study (<50, \geq 50)
- Clinical reader and SOT classification certainty (1 to 5)

The number of clinical readers in the above subgroups will be provided. The number and percentage of diagnostic accuracy categories <70%, >70% to \leq 80%, >80% to \leq 90%, and >90% will also be provided by using the above subgroups for prospective images, retrospective images, and pooled results, separately.

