9.5 Study Size

Number of Subjects

This study has no formal hypothesis and no statistical tests will be performed. The endpoints of accuracy, sensitivity, and specificity will be summarised descriptively with point estimates and

95% CIs. Although no formal hypothesis will be tested, the sample size is determined to achieve the desired precision in estimating the primary endpoint of the percentage of subjects whose images are correctly classified as positive or negative (accuracy). Assuming that VIZAMYLTM images from 90% of subjects are read correctly by readers who have taken the VIZAMYLTM training programme, 200 subjects will achieve a 95% CI width of less than 10%.

The endpoints of sensitivity and specificity will also be summarised descriptively. This study aims to characterise reader performance in clinical practice so the number of positive and negative images will not be controlled. However, it is expected that most patients who are referred for a VIZAMYLTM scan will have dementia, and most cases of dementia are AD. Since brain amyloid is present in AD, it is expected that the majority of patients in this study will have brain amyloid. It is assumed that the majority blinded interpretation of the expert readers will be SOT-positive for approximately 65% of scans, giving a total of approximately 130 scans for sensitivity, with the remaining 70 scans being SOT-negative and therefore usable for calculating specificity. Assuming a sensitivity of 90% and a specificity of 90%, these sample sizes should give reasonably precise 95% CIs for estimating sensitivity and specificity in this scenario (95% CI width of approximately 15% or less).

Accuracy, sensitivity, and specificity will also be calculated by country where all study images from sites within a given country will be pooled for analysis. No country may contribute more than 25% of the total number of images. Because the number of subjects per country is smaller than the overall number of subjects, the level of precision and the width of the CI will be impacted. Again, since the aim of the study is to characterise reader performance in clinical practice, the exact number of images obtained per country and per site is unknown. Table 6 provides examples of 95% CI widths for accuracy assuming a few different sample sizes per country to illustrate the change in precision.

Table 6 95% Confidence Interval Width for Different Sample Sizes Assuming 90% Diagnostic Accuracy

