The by-variable summaries will include estimates of diagnostic accuracy, sensitivity, specificity, PPV, and NPV along with 95% CIs for data pooled within each category. They will also show the number of clinical readers in each category and the number and percentage of clinical readers in each category with diagnostic accuracy <70%, >70% to $\le80\%$, >80% to $\le90\%$, and >90%.

The certainty of image classification will be summarised.

Safety Analyses

The number and percentage of subjects with 1 or more treatment-emergent AEs will be summarised. Additionally, treatment-emergent AEs will be coded and summarised by system organ class and preferred term. Treatment-emergent AE summaries will be provided by relationship to study drug and severity. Treatment-emergent serious AEs (SAEs) will also be summarised.

Interim Analysis

No formal interim analyses of the data are planned for this study. Interim progress reports of enrolment and safety will be provided annually.

Analyses of Study Limitations

Please see Section 9.9 below.

Evaluation of Impact of Study Results on Marketing Authorisation

The Sponsor will evaluate whether the study results have an impact on the marketing authorisation and will, if necessary, submit to the EMA an application to vary the marketing authorisation.

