2.2 Secondary objectives

Evaluate the impact of demographic and other factors (such as method of training, gap between training and reading, and country) on diagnostic accuracy to try to identify factors that may be associated with image interpretation errors.

Sensitivity is the true-positive (TP) image interpretation rate in subjects with brain amyloid. Specificity is the true-negative (TN) image interpretation rate in subjects without brain amyloid. Positive predictive value (PPV) is the TP image interpretation rate for subjects with positive VIZAMYL™ scans. Negative predictive value (NPV) is the TN image interpretation rate for subjects with negative VIZAMYL™ scans.

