5 SAMPLE SIZE AND POWER

Number of Subjects

This study has no formal hypothesis and no statistical tests will be performed. The endpoints of accuracy, sensitivity, and specificity will be summarised descriptively with point estimates and 95% CIs. Although no formal hypothesis will be tested, the sample size is determined to achieve the desired precision in estimating the primary endpoint of the percentage of subjects whose images are correctly classified as positive or negative (accuracy). Assuming that VIZAMYL™ images from 90% of subjects are read correctly by readers who have taken the VIZAMYL™ training programme, 200 subjects will achieve a 95% CI width of less than 10%.

The endpoints of sensitivity and specificity will also be summarised descriptively. This study aims to characterise reader performance in clinical practice so the number of positive and negative images will not be controlled. However, it is expected that most patients who are referred for a VIZAMYL™ scan will have dementia, and most cases of dementia are Alzheimer's Disease (AD). Since brain amyloid is present in AD, it is expected that the majority of patients in this study will have brain amyloid. It is assumed that the majority blinded interpretation of the expert readers will be SOT-positive for approximately 65% of scans, giving a total of approximately 130 scans for sensitivity, with the remaining 70 scans being SOT-negative and therefore usable for calculating specificity. Assuming a sensitivity of 90% and a specificity of 90%, these sample sizes should give reasonably precise 95% CIs for estimating sensitivity and specificity in this scenario (95% CI width of approximately 15% or less).

Accuracy, sensitivity, and specificity will also be calculated by country where all study images from sites within a given country will be pooled for analysis. No country may contribute more than 25% of the total number of images. Because the number of subjects per country is smaller than the overall number of subjects, the level of precision and the width of the CI will be impacted. Again, since the aim of the study is to characterise reader performance in clinical practice, the exact number of images obtained per country and per site is unknown. [Table 5-1](#) provides examples of 95% CI widths for accuracy assuming a few different sample sizes per country to illustrate the change in precision.

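### PPV and NPV by country and reader factor cannot be compared across categories whose share of amyloid-positive scans differs, and crude accuracy only partly; the tables should show that share and standardise accuracy to it

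*SAP*

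**What the plan says.** The secondary objective (Protocol 8, SAP 2.2) is to evaluate the impact of factors such as training method, gap since training and country "on diagnostic accuracy to try to identify factors that may be associated with image interpretation errors". It is therefore framed on accuracy.

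SAP 8.6.3 meets it with tables by category: "estimates of diagnostic accuracy, sensitivity, specificity, PPV, and NPV, along with exact 95% CIs, will be provided separately" for prospective, retrospective and pooled images. Protocol 9.7 promises the same five measures, ending "NPV along with 95% CIs for data pooled within each category". Both sections also sort results into accuracy bands, from below 70% to above 90%. Neither describes standardisation, stratification by SOT status or a model.

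On the mix of scans, Protocol 9.5 states that "the number of positive and negative images will not be controlled"; SAP section 5 repeats this. The planning value for the whole study is "SOT-positive for approximately 65% of scans, giving a total of approximately 130 scans for sensitivity". Reader performance is taken as equal on both sides: "Assuming a sensitivity of 90% and a specificity of 90" per cent. SAP 8.6.2 summarises positive and negative classifications but does not call for this by factor category. The limitations in Protocol 9.9 mention imbalance among reader subgroups, but not differences in the share of positive scans.

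**The concern.** Sensitivity and specificity are calculated within SOT-positive and SOT-negative scans, so the share of positives does not enter them directly. PPV and NPV mix the two groups and depend on the share by construction. Accuracy is the average of sensitivity and specificity weighted by the share.

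The share can plausibly differ between categories. Protocol 9.2 admits primary, secondary and tertiary settings and expects many referrals for atypical or early-onset cases. Two countries, or two training methods, could then show different NPV with equally skilled readers. In a table meant to point to sources of misreading, that gap can be taken for a reader or training effect. The reverse is also possible: a difference in mix could mask a real difference in performance.

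**Working it through.** **Inputs.** From the documents: sensitivity (Se) and specificity (Sp) both 90%, SOT-positive share (p) 65%, 200 images, at most 50 per country. Assumed here, because the documents give no range: category shares from 50% to 80%, and the unequal pairs Se/Sp = 95%/80% and 85%/95%. Unequal performance is not far-fetched: Protocol 7 reports one reader in study GE067-007 with high sensitivity but lower specificity.

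**The plan's own figures.** Clopper-Pearson 95% intervals at 90% reproduce the SAP table: widths of 24.4, 20.9, 18.5 and 16.7 points at 30, 40, 50 and 60 images. The 40-image country example also reproduces: 26.4 points for sensitivity (26 scans) and 37.0 for specificity (14 scans). At 200 images the interval is 85.0% to 93.8%, a width of 8.8 points, as the SAP expects ("200 subjects will achieve a 95% CI width of less than 10" per cent).

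**Formulas.**
- Accuracy = p·Se + (1−p)·Sp
- PPV = p·Se / [p·Se + (1−p)(1−Sp)]
- NPV = (1−p)·Sp / [(1−p)·Sp + p(1−Se)]

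**Example.** At 90%/90% and p = 0.80, NPV = 0.18 / (0.18 + 0.08) = 69.2% and PPV = 0.72 / (0.72 + 0.02) = 97.3%.

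**Results with reader performance held fixed (%).**

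| SOT-positive share | NPV, 90/90 | PPV, 90/90 | Accuracy, 90/90 | Accuracy, 95/80 (assumed) | Accuracy, 85/95 (assumed) |
|---|---|---|---|---|---|
| 50 | 90.0 | 90.0 | 90.0 | 87.5 | 90.0 |
| 65 | 82.9 | 94.4 | 90.0 | 89.8 | 88.5 |
| 80 | 69.2 | 97.3 | 90.0 | 92.0 | 87.0 |

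From 50% to 80% positive, NPV falls by 20.8 points and PPV rises by 7.3. Accuracy changes by (Se − Sp) times the change in share: 0 at 90/90; 0.15 × 0.30 = +4.5 points at 95/80; −0.10 × 0.30 = −3.0 points at 85/95. At 95/80, expected accuracy crosses from the band above 80% and up to 90% into the band above 90%, with no change in skill.

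**Effect of standardising.** With the weight fixed at the planned 65%, accuracy at 95/80 is 0.65 × 0.95 + 0.35 × 0.80 = 89.8% in every category, whatever its own mix. The other two pairs give 90.0% and 88.5%.

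**The case against.** The case on the other side is substantial, and most of it stands as a limit on the point.

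- A reader might infer that the factor tables rest only on measures that depend on case mix. They do not: sensitivity and specificity are listed in the same sentence. What is missing is a statement that comparisons between categories rest on them.
- The secondary objective names accuracy, not PPV or NPV, and the large shifts belong to the latter. Under the plan's 90%/90% accuracy does not move at all. In the unequal cases above it moves 3 to 4.5 points, against an exact interval 18.5 points wide for a country at the 50-image cap. The shift is systematic and the interval does not allow for it, but it is small.
- It is tempting to say that chance alone will produce wide differences in mix. With a true share of 65%, the central 95% range for a 30-image country is 14 to 24 positives (47% to 80%). However, two such countries differ by 10 or more positives only about 1% of the time.
- The printed intervals already signal caution. For 50 images at 80% positive with 90%/90% readers, NPV is 9/13 = 69.2%, with an exact interval of 38.6% to 90.9%.
- The share may be recoverable. SAP 8.6.1 provides for counts where applicable, SAP 8.6.2 plans subject-level listings, and the table templates are in a separate document. It is not established that the share will be absent from the output; the plan just does not require it.
- Saying that case mix will be reported as a cause goes beyond the documents. The study is descriptive, has no tests, and looks for association. An association with errors can still arise from the mix alone.

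**Conclusion.** The point holds in a limited form. Crude PPV and NPV are not comparable between categories with different SOT-positive shares, and nothing in the SAP or protocol says so. At the plan's own performance values the NPV gap is 20.8 points over an assumed 50% to 80% range. Crude accuracy and the accuracy bands are affected only when sensitivity and specificity differ, and modestly: 4.5 points at an assumed 95%/80%.

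The sizes rest on the assumed range of shares and the assumed unequal pairs; the direction for PPV and NPV does not. Sensitivity and specificity could still vary with the difficulty of the scans, such as the number of borderline cases, and no reweighting by share would correct that. The pooled primary estimates are untouched. This is a minor improvement to the secondary analysis.

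**What to change.** In SAP 8.6.3 and Protocol 9.7:

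1. Print the number and percentage of SOT-positive scans for every category, in the prospective, retrospective and pooled columns.
2. Beside crude accuracy, give accuracy standardised to the pooled SOT-positive share p: p·Se + (1−p)·Sp, using the category's own Se and Sp.
3. State that comparisons between categories rest on sensitivity, specificity and standardised accuracy, and that crude PPV and NPV by category are descriptive and not for comparison.

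The cost is one paragraph and a few table columns; every image is already classified as TP, TN, FP or FN. The downside is imprecision where a category has few SOT-negative scans. With 40 images at 80% positive there are 8 such scans. One misread among them moves standardised accuracy by 0.35/8 = 4.4 points (at the planned 65% share), against 1/40 = 2.5 points for crude accuracy. Where a category lacks SOT-positive or SOT-negative scans, standardised accuracy cannot be calculated and the table should say so.

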8.7 Safety analyses

8.7.1 Adverse events

All AEs will be classified by primary system organ class (SOC) and preferred term (PT) according to the Medical Dictionary for Regulatory Activities (MedDRA).

A treatment-emergent AE (TEAE) is defined as an AE that begins or worsens in severity after at least one dose of study treatment has been administered.

AE summary tables will be presented for TEAEs only and will include the following:

- All TEAEs
- Subject with at least one TEAE
- Related TEAEs
- TEAEs by maximum severity
- Serious TEAEs

An overall summary for the above categories will be presented. All TEAEs categories presented above will also be summarised by SOC and PT using frequency counts and percentages (i.e., number and percentage of subjects with an event). The safety population will be used for these summaries.

If a subject has the same AE, based on PT, reported multiple times in the treatment period, the subject will only be counted once at the PT level in AE frequency tables.

If a subject has multiple AEs within the same SOC in the treatment period, the subject will only be counted once at the SOC level in the AE frequency tables.

When reporting AEs by severity, in addition to providing a summary table based on the event selection criteria detailed above, a summary table will also be provided based on the most intense event during the treatment period, independent of relationship to study treatment.

In the summaries by SOC and PT, AEs will be sorted by decreasing frequency within each SOC and PT within each SOC.

Individual listings will be provided for AEs.

8.7.2 Clinical laboratory evaluations

No laboratory assessment will be done.

8.7.3 Vital signs

No vital assessment will be done.

8.7.4 Physical examinations

No assessment will be done.

8.7.5 Electrocardiograms

No assessment will be done.

8.8 Interim analysis

No formal interim analyses (IA) of the data are planned for this study.

**9 CHANGES TO PLANNED ANALYSIS FROM STUDY
 PROTOCOL**

No change in protocol planned analysis.

11 APPENDICES

Not applicable
